Prospective, Multi-Center, Randomized Controlled Trial for Skeletal Age Assessment AI Model

Study Protocol and Statistical Analysis Plan

NCT03530098

August 1, 2018

Clinical Research Protocol
SKELETAL AGE ASSESSMENT AI MODEL

Protocol Number:	1
Version Date:	August 2018
Investigational Device:	Skeletal age assessment AI model
IND Number:	N/A
Development Phase:	N/A
Sponsor:	N/A
Funding Organization:	N/A
Principal Investigator:	Name: [name]. E-mail: [contact] [contact] Name: [name]., M.P.H. E-mail: [contact] [contact]
Medical Monitor:	N/A
Coordinating Center:	Stanford University

PROTOCOL SYNOPSIS

TITLE	Prospective, Multi-Center, Randomized Controlled Trial for Skeletal Age Assessment AI Model
SPONSOR	N/A
FUNDING ORGANIZATION	N/A
NUMBER OF SITES	6
RATIONALE	To determine whether the AI model improves radiologist performance.
STUDY DESIGN	This is a prospective, multi-center, randomized controlled trial with two arms: Experiment and Control. Radiologists receive the AI model for studies randomized into the Experiment arm before dictating a final impression.
PRIMARY OBJECTIVE	To determine whether radiologists are more accurate at assessing skeletal age using the AI model, compared to not using the AI model.
SECONDARY OBJECTIVES	To determine whether radiologists are more efficient at assessing skeletal age using the AI model, compared to not using the AI model.
NUMBER OF SUBJECTS	1600 interpretations by consented radiologists.
SUBJECT SELECTION CRITERIA	
Inclusion Criteria:
 
 1. Verbal informed consent obtained from interpreting radiologist. 2. Procedure code or study description indicative of hand radiograph for skeletal age assessment. 
Exclusion Criteria:
 
 1. Trainee provided a preliminary interpretation.
TEST DEVICE, DEPLOYMENT	The AI model will populate the radiologists' report templates.
CONTROL DEVICE, DEPLOYMENT	The AI model will not populate the radiologists' report templates.
DURATION OF STUDY	Estimated to be 6 months from the start date.
CONCOMITANT MEDICATIONS	N/A
EFFICACY EVALUATIONS	N/A

PRIMARY ENDPOINT	
 • Mean absolute difference between dictated final impressions and the consensus determination of a panel of radiologists.
SECONDARY ENDPOINTS	
 • Radiologist interpretation time.
OTHER EVALUATIONS	N/A
SAFETY EVALUATIONS	Since the device does not pose greater than minimal risk, neither an adverse event (AE) or serious adverse experience (SAE) is expected. Unanticipated risks will be reported to the IRB, in accordance with IRB standards.
PLANNED INTERIM ANALYSES	N/A
STATISTICS Primary Analysis Plan	
 1. Detect differences in the primary endpoint between Experiment and Control arms, using a two-sided Student t-test. 2. Detect differences in the secondary endpoint between Experiment and Control arms, using a Wilcoxon rank-sum test.
Rationale for Number of Subjects	Targeting a power of 0.75, statistical tests achieved a power of 0.79 to detect a difference of 0.50 months for 1600 interpretations.

1 BACKGROUND

Radiologists perform a skeletal age assessment to determine the developmental status of a pediatric patient. We trained an AI model on the open-source RSNA dataset to predict the skeletal age from a hand radiograph and intend to determine the effect of its clinical use in a prospective, multi-center, randomized controlled trial.

1.1 Overview of Non-Clinical Studies

Previous work from Larson, et al. [1] suggests that using an AI model as a diagnostic aid could improve the quality of skeletal age assessment.

[1] Larson, et al. "Performance of a Deep-Learning Neural Network Model in Assessing Skeletal Maturity on Pediatric Hand Radiographs" (2017).

1.2 Overview of Clinical Studies

To our knowledge, there do not exist previous clinical studies in the form of a prospective clinical trial of any AI model.

2 STUDY RATIONALE

Though the AI model from Larson, et al. [1] performs as well as human radiologists in controlled settings, it remains uncertain whether use of an AI model as a diagnostic aid can improve the quality of skeletal age assessment in true clinical settings.

3 STUDY OBJECTIVES

3.1 Primary Objective

The primary objective is to determine the effect of using an AI model as a diagnostic aid for skeletal age assessment on the quality of radiologists' interpretations, as measured by the mean absolute difference between their dictated final impressions and the consensus determination of a panel of radiologists.

3.2 Secondary Objectives

The secondary objective is to determine the effect of using an AI model as a diagnostic aid for skeletal age assessment on the efficiency of radiologists' interpretations, as measured by their interpretation times.

4 STUDY DESIGN

4.1 Study Overview

This is a prospective, multi-center, randomized controlled trial. 1600 interpretations by consented radiologists are planned.

Each of the interpreted studies will be assigned at random to one of two arms: Experiment or Control. The AI model will populate the radiologists' report templates for studies assigned to the Experiment arm. The AI model will not populate the radiologists' report templates for studies assigned to the Control arm.

5 CRITERIA FOR EVALUATION

5.1 Primary Efficacy Endpoint

The primary endpoint is mean absolute difference between dictated final impressions and the consensus determination of a panel of radiologists.

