8.2 Blinding

Due to the objectives of the study, the identity of Experiment and Control treatment groups will be known to radiologists.

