9 STUDY PROCEDURES AND GUIDELINES

A Schedule of Events representing the required testing procedures to be performed for the duration of the study is diagrammed in Appendix 1.

Prior to conducting any study-related activities, verbal informed consent must be obtained from the radiologist. In addition, written informed consent by the patient must be waived by the IRB.

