10 EVALUATIONS BY VISIT

The device records individual visits.

1. Receive the study as a DICOM file.
2. Record the study as a DICOM file.
3. Randomizes the study.
4. Perform and record the AI model.
5. If randomized into the Experiment arm, populate the radiologists' report template with the AI model.

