APPENDIX 1. SCHEDULE OF EVENTS

	REQUIRED
Install Device	X
Informed Consent	X
Test Device	X
Begin Randomization	X
End Randomization	X
Collect Data from Device	X

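### Does silence about how the radiologist panel reads, and whether it is masked, undermine the primary endpoint?

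*Combined protocol and SAP*

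**What the plan says.** The panel is named in the synopsis, in Section 3.1 and in Section 5.1, where the endpoint is defined: "The primary endpoint is mean absolute difference between dictated final impressions and the consensus determination of a panel of radiologists". Its size, membership, consensus rule, timing and reading material are not given.

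Section 9 points to the schedule: "A Schedule of Events representing the required testing procedures to be performed for the duration of the study is diagrammed in Appendix 1". Appendix 1 lists six events, the last being "Collect Data from Device". None is a panel reading.

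Section 10 lists five device steps. The image is recorded at step 2 and randomization is step 3. Step 4, "Perform and record the AI model", applies to every study. Only step 5 depends on arm: "If randomized into the Experiment arm, populate the radiologists' report template with the AI model".

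Section 8.2 is the only text on blinding: "Due to the objectives of the study, the identity of Experiment and Control treatment groups will be known to radiologists". It does not mention the panel.

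**The concern.** The intervention is open to the interpreting radiologist, and the reference is itself a human judgement. The independence of that reference is therefore the main protection for the primary comparison. Three facts together look troubling: nothing masks the panel, AI output exists for Control as well as Experiment studies, and the one collection event in Appendix 1 draws on the device that holds that output.

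Equal exposure in both arms would not cancel. If the panel leaned toward the AI everywhere, Experiment would gain, because only its reports start from the AI value. A lean toward the dictated reports would instead shrink a true difference. The planned t-test takes the reference as given and would not flag either. With a planned difference of only 0.50 months, a modest lean could matter.

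**Working it through.** **Reading the text**

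- *Blinding.* Section 8.2 ties the open assignment to the study's objectives. Those objectives concern radiologists reading with and without the AI in their templates, so the sentence most naturally means the interpreting radiologists. It neither unmasks nor masks the panel.
- *Schedule.* Appendix 1 lists set-up and running events. It also leaves out the dictation, the interpretation time, the demographics and the medical history. Section 10 describes only what the device does. A missing panel row is therefore not particular to the panel and does not show that the reading will not happen.
- *Route from AI to panel.* None is described. The image and the AI output are recorded in separate steps, so the image can be shown without the AI value. It is stored before randomization.

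**The plan's own figure**

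Inputs from Sections 8.1, 14.3 and 14.6: 1:1 allocation of 1600 interpretations (800 per arm), a two-sided t-test, and power 0.79 for 0.50 months. Alpha and SD are not stated, so 0.79 cannot be reproduced independently; it can only be solved backwards.

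- At two-sided alpha 0.05 (assumed): SE = 0.50/(1.960 + 0.806) = 0.181 months.
- SD = SE/√(2/800) = 0.1807/0.05 = 3.61 months.
- For alpha 0.01 to 0.10: SE 0.148 to 0.204, SD 2.96 to 4.08 months.

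**Spurious difference in the endpoint**

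With no true effect, P(significant) = Φ(b/SE − 1.96) + Φ(−b/SE − 1.96), where b is a spurious difference in *mean absolute difference*.

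| b (months) | P(significant) |
|---|---|
| 0.10 | 0.086 |
| 0.25 | 0.282 |
| 0.50 | 0.79 |

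These rates do not apply to a constant shift of the reference itself. If the signed difference is normal with mean zero, its SD is σ = 3.61/√(1 − 2/π) = 6.0 months, and the mean absolute difference is 6.0 × √(2/π) = 4.78 months. Moving one arm's reference by a constant 0.5 months changes the mean absolute difference by about 0.5² × 0.399/6.0 = 0.017 months. The false-positive rate is then 0.051.

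**Equal lean toward dictated reports**

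If the reference moves a fraction 0.10 toward the report in both arms, every absolute difference is multiplied by 0.90. A true 0.50 becomes 0.45 months and the SE becomes 0.90 × 0.181 = 0.163. The ratio is 2.77 before and after. The estimate shrinks, but the test and its power do not change.

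**Equal lean toward the AI**

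Assumptions: AI error variance equals reader error variance, with error correlation ρ; readers keep the AI value in a fraction q = 0.5 of Experiment studies; the panel moves a fraction w toward the AI in both arms; panel error is a share s of the total variance. Then

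bias = q × 4.78 × [√((1−s)(1 + w² − 2wρ) + s(1−w)²) − (1−w)].

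| ρ | s | w | bias (months) | false-positive rate |
|---|---|---|---|---|
| 0 | 0 | 0.10 | 0.251 | 0.285 |
| 0 | 0 | 0.05 | 0.123 | 0.104 |
| 0 | 0.5 | 0.05 | 0.062 | 0.064 |
| 0.3 | 0.25 | 0.10 | 0.135 | 0.116 |
| 0.5 | 0.5 | 0.05 | 0.031 | 0.053 |

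The first row assumes a panel that makes no error yet still moves toward the AI, and AI and reader errors that are unrelated although both judge the same film. Relaxing both (ρ 0.3 to 0.5, s 0.25 to 0.5) gives 0.031 to 0.135 months. With w = 0, which is what a masked read means, the bracket is √1 − 1 = 0 for any s and ρ.

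**The case for a change.** The strongest case for a change is that the trial is open-label, the AI value is placed in the report template, and the reference is human, so independence of the panel should be written down. Writing it down would be cheap, because the images are already held, and analysis alone cannot restore independence after an unmasked read. The direction of the risk is also clear: a lean toward the AI favours Experiment.

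Much of this stands. The omission is certain, the mechanism is real, and a sentence on masking would do no harm. Two parts do not stand. The schedule argument proves too much, since the same listing also leaves out the dictated impression and the secondary endpoint. It is also too strong to say that a benefit could never be separated from panel–AI agreement. The stored images and AI values cover both arms, so a masked re-read of a sample could test it.

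The assumption of equal AI accuracy is weak as well. Section 2 says of an earlier, cited model that it "performs as well as human radiologists in controlled settings"; it does not say so of the model in this trial.

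**Conclusion.** The concern does not call for a change to the plan. The documents name a panel consensus and leave its conduct unstated. No rule in them shows the panel the arm, the AI output or the report. Investigators who follow the plan and have the panel read the stored images masked, which is ordinary practice for a reference reading, obtain a sound primary endpoint.

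The possible bias is conditional. It runs from about 0.03 to 0.25 months if the panel leaned 5% to 10% toward the AI, and from about 0.03 to 0.135 months once AI and reader errors are correlated and the panel has error of its own. These figures rest on assumed alpha 0.05, back-solved SD 3.6 months, normal errors, equal AI and reader accuracy, and the AI value kept in half of Experiment studies. An equal lean toward dictated reports leaves the t-test unchanged. The conclusion would differ if a study document stated that the panel works with the AI value or the dictated report in view; these documents do not.

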5.2 Secondary Efficacy Endpoints

- Radiologist interpretation time.

5.3 Safety Evaluations

- Since the device does not pose greater than minimal risk, neither an adverse event (AE) or serious adverse experience (SAE) is expected. Unanticipated risks will be reported to the IRB, in accordance with IRB standards.

6 SUBJECT SELECTION

6.1 Study Population

Radiologists who interpret hand radiographs for skeletal age assessment will be eligible for participation in this study. Studies that meet the inclusion and exclusion criteria will be eligible for this study.

6.2 Inclusion Criteria

1. Verbal informed consent obtained from interpreting radiologist.
2. Procedure code or study description indicative of hand radiograph for skeletal age assessment.

6.3 Exclusion Criteria

1. Trainee provided a preliminary interpretation.

7 CONCURRENT MEDICATIONS

The study does not involve medications or chronic therapies.

8 STUDY TREATMENTS

8.1 Method of Assigning Subjects to Treatment Groups

Studies will be assigned at random to Experiment or Control treatment groups in a 1:1 ratio using the Python random package.

8.2 Blinding

Due to the objectives of the study, the identity of Experiment and Control treatment groups will be known to radiologists.

8.3 Formulation of Test and Control Products

The study does not involve test or control devices. The Control arm represents the absence of any intervention and is consistent with the current standard of care.

8.4 Supply of Study Device at the Site

The device will be installed at the investigational sites one time prior to randomization by the Investigator. The device will receive studies from the sites, perform randomization, and populate the radiologists' report templates for studies assigned to the Experiment arm for the duration of the study.

9 STUDY PROCEDURES AND GUIDELINES

A Schedule of Events representing the required testing procedures to be performed for the duration of the study is diagrammed in Appendix 1.

Prior to conducting any study-related activities, verbal informed consent must be obtained from the radiologist. In addition, written informed consent by the patient must be waived by the IRB.

9.1 Clinical Assessments

9.1.1 Concomitant Medications

The study does not require documentation of concomitant medication or concurrent therapies.

9.1.2 Demographics

Demographic information (date of birth, gender, race) will be collected retrospectively.

9.1.3 Medical History

Relevant medical history, including history of current disease, other pertinent history, and information regarding underlying diseases will be collected retrospectively.

9.1.4 Physical Examination

The study does not require a physical examination.

9.1.5 Vital Signs

The study does not require body temperature, blood pressure, pulse and respirations.

9.1.6 Adverse Events

Since the device does not pose greater than minimal risk, neither an adverse event (AE) or serious adverse experience (SAE) is expected. Unanticipated risks will be reported to the IRB, in accordance with IRB standards.

9.2 Clinical Laboratory Measurements

The study does not require clinical laboratory measurements.

10 EVALUATIONS BY VISIT

The device records individual visits.

1. Receive the study as a DICOM file.
2. Record the study as a DICOM file.
3. Randomizes the study.
4. Perform and record the AI model.
5. If randomized into the Experiment arm, populate the radiologists' report template with the AI model.

11 ADVERSE EXPERIENCE REPORTING AND DOCUMENTATION

11.1 Adverse Events

An adverse event (AE) is any untoward medical occurrence in a clinical investigation of a patient administered a pharmaceutical product and that does not necessarily have a causal relationship with the treatment. An AE is therefore any unfavorable and unintended sign (including an abnormal laboratory finding), symptom or disease temporally associated with the administration of an investigational product, whether or not related to that investigational product.

The device is not a pharmaceutical product.

Since the device does not pose greater than minimal risk, an adverse event (AE) is not expected. Unanticipated risks will be reported to the IRB, in accordance with IRB standards.

11.2 Serious Adverse Experiences (SAE)

An SAE is defined as any AE occurring at any dose that results in any of the following outcomes:

- death
- a life-threatening adverse experience
- inpatient hospitalization or prolongation of existing hospitalization
- a persistent or significant disability/incapacity
- a congenital anomaly/birth defect

Other important medical events may also be considered an SAE when, based on appropriate medical judgment, they jeopardize the subject or require intervention to prevent one of the outcomes listed.

The device is not a pharmaceutical product.

Since the device does not pose greater than minimal risk, a serious adverse experience (SAE) is not expected. Unanticipated risks will be reported to the IRB, in accordance with IRB standards.

12 DISCONTINUATION AND REPLACEMENT OF SUBJECTS

12.1 Early Discontinuation of Study Device

A radiologist may be discontinued from study treatment at any time if the radiologist or the Investigator feels that it is not in the radiologist's best interest to continue.

All radiologists are free to withdraw from participation at any time, for any reason, specified or unspecified, and without prejudice.

Reasonable attempts will be made by the Investigator to provide a reason for radiologist withdrawals.

12.3 Withdrawal of Subjects from the Study

A radiologist may be withdrawn from the study at any time if the radiologist or the Investigator feels that it is not in the radiologist's best interest to continue.

All radiologists are free to withdraw from participation at any time, for any reason, specified or unspecified, and without prejudice.

Reasonable attempts will be made by the Investigator to provide a reason for radiologist withdrawals.

12.4 Replacement of Subjects

Radiologists who withdraw from the study treatment will not be replaced.

Radiologists who withdraw from the study will not be replaced.

13 PROTOCOL VIOLATIONS

A protocol violation occurs when the radiologist or Investigator fails to adhere to significant protocol requirements affecting the inclusion, exclusion, radiologist safety and primary endpoint criteria. Protocol violations for this study include, but are not limited to, the following:

- Failure to meet inclusion/exclusion criteria

Failure to comply with Good Clinical Practice (GCP) guidelines will also result in a protocol violation. The Investigator will determine if a protocol violation will result in withdrawal of a radiologist.

When a protocol violation occurs, it will be discussed with the Investigator and a Protocol Violation Form detailing the violation will be generated.

14 STATISTICAL METHODS AND CONSIDERATIONS

14.1 Data Sets Analyzed

Studies that meet the inclusion and exclusion criteria will be included the analysis.

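### Could exclusions made after randomization under section 14.1 bias the arm comparison without anyone noticing?

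*Combined protocol and SAP*

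**What the plan says.** Section 14.1 gives one rule for the analysis set: "Studies that meet the inclusion and exclusion criteria will be included the analysis". It defines no set of all randomized studies and asks for no exclusion counts by arm, and the rest of section 14 adds neither.

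The criteria are of two kinds. The procedure code or study description (6.2, item 2) is known when the images arrive. The other two depend on the reading: section 6.3 excludes a study if "Trainee provided a preliminary interpretation", and section 6.2, item 1, requires "Verbal informed consent obtained from interpreting radiologist".

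On sequence, section 8.4 says "The device will receive studies from the sites, perform randomization, and populate" the templates for Experiment studies. Section 10 lists the device steps: after receipt comes "Record the study as a DICOM file", then "Randomizes the study", then running the model, then filling the template in the Experiment arm. No eligibility check is listed. Section 8.2 says "the identity of Experiment and Control treatment groups will be known to radiologists". Section 4.1 says "Each of the interpreted studies will be assigned at random to one of two arms", which taken literally puts interpretation ahead of assignment.

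Three other places bear on the point. Section 6.1 makes only criteria-meeting studies eligible. Section 9 puts radiologist consent ahead of any study activity. Section 13 treats an eligibility failure as a protocol violation, to be documented on a form.

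**The concern.** Randomization protects the comparison only if the studies analysed are the studies assigned, or if those dropped are dropped for reasons unconnected with the arm. Here the device appears to assign the arm on receipt, while a trainee's preliminary read, or the identity of the interpreting radiologist, may be settled later by people who can see whether the template has been filled. If a pre-filled template made it less likely that a trainee drafted the read, or steered cases between consented and non-consented readers, the t-test in section 14.3 would compare groups selected after assignment. The bias could run either way. The target difference is only 0.50 months (section 14.6), so a modest shift would matter, and nothing planned in section 14 would reveal it.

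**Working it through.** **1. The plan's own figure.** Section 14.6 gives power 0.79 for 0.50 months with 1600 interpretations, so 800 per arm at 1:1 (section 8.1). No SD or alpha is stated, so the figure can only be back-solved, not reproduced independently.

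- Two-sided alpha 0.05 (assumed): SE = 0.50 / (1.960 + 0.806) = 0.181. SD = SE × √(800/2) = 0.181 × 20, about 3.61 months.
- Two-sided alpha 0.10 (alternative): SE = 0.50 / (1.645 + 0.806) = 0.204, SD about 4.08 months.

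**2. Bias from unequal exclusion.** Let p be the share excluded in an arm and g the mean absolute error of excluded studies minus that of retained ones, equal in both arms. The retained mean is the overall mean minus p × g, so the arm contrast shifts in size by |pE − pC| × |g|. The false-positive rate is P(|Z + bias/SE| > z). Every p and g below is an assumption; the documents give none.

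| Gap in exclusion rate | g (months) | Bias (months) | False-positive rate, alpha 0.05 | Alpha 0.10 |
|---|---|---|---|---|
| 0 points | any | 0 | 0.050 | 0.100 |
| 5 points | 1 | 0.05 | 0.059 | 0.110 |
| 10 points | 2 | 0.20 | 0.198 | 0.258 |

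The table takes 800 analysed per arm. If instead 800 per arm are randomized and 15% and 5% are excluded, 680 and 760 remain. Then SE = 3.61 × √(1/680 + 1/760) = 0.191, and the last row at alpha 0.05 falls to about 0.18.

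In the other direction, a true 0.50 months is seen as 0.45 or 0.30, and power falls from 0.79 to 0.70 or 0.38.

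The last row needs a 2-month error gap, which is 2/3.61 = 0.55 of the implied SD, together with a 10-point difference between arms.

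**3. What counts by arm would and would not show.** With 800 per arm, exclusion of 5% v 10% gives a 95% CI half-width of 1.96 × √(0.05×0.95/800 + 0.10×0.90/800) = 2.6 points, and power 0.97 to detect the gap. But if 10% are excluded in both arms and only one arm loses studies that are 2 months harder, the bias is 0.10 × 2 = 0.20 months. With 720 retained per arm the false-positive rate is about 0.18, and the counts look balanced. Counts therefore help but do not settle the matter; the characteristics of the excluded studies are needed too.

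**4. Cost of analysing trainee-read studies as well.** If they make up a share f of randomized studies, the extra panel reads are 1600/(1 − f) − 1600, which is 84 at f = 5% and 178 at f = 10% (f assumed). If the AI model has no effect in them, the expected difference dilutes to 0.50 × 0.95 = 0.475 or 0.50 × 0.90 = 0.45 months.

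**5. Order of events.** The synopsis (study design) has the radiologist receive the model output for Experiment studies ahead of the final dictation. Section 4.1 itself goes on to describe template filling as following assignment. Section 10 agrees. Assignment therefore precedes the final read throughout, and the word about interpreted studies in section 4.1 is loose wording for the studies in the trial.

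**The case for a change.** The strongest case for a change is that each factual part is in the text. There is no screening step before randomization, the one exclusion criterion describes a reading event, the design is open to the reader, and section 14 plans nothing that would expose a differential loss. Section 6.1 does not say when eligibility is checked. Section 13 produces a form but no tabulation by arm. Withdrawal at any time (sections 12.1 and 12.3) keeps the consent criterion partly open despite section 9. On this view the defect is not that bias has been shown but that it could not be seen.

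The omission stands: the timing of the check and the flow by arm are not written down. Its weight does not carry over. Section 10 lists what the device does, not what the sites do before sending a study, so silence there does not establish when the criteria are applied. Even if a trainee read is identified only after assignment, bias needs that read to depend on the arm. Section 8.2 does not say when radiologists learn the arm, and it mentions neither trainees nor case assignment.

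Nor would the gap stay hidden in practice. Anyone forming the section 14.1 set after randomization must hold the arm, the trainee status and the reader's consent status for every study the device randomized, so a flow table by arm and reason comes from the same data. If sites filter before sending, there are no such exclusions to report.

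The costlier proposal, a sensitivity analysis that restores trainee-read studies, answers a different question. Section 6.3 removes them by design, they would need additional panel reads, and readings by non-consented radiologists would still be left out. Writing it into this combined document would also need prior IRB approval under section 16.1.

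**Conclusion.** No change to the plan is called for. The route to bias exists in principle, but no section shows that it is used, and its size cannot be derived from the documents. On assumed inputs it ranges from nothing, with exclusions unrelated to arm, through a false-positive rate of 0.059 for a 5-point gap and 1 month, to about 0.18 to 0.20 for a 10-point gap and 2 months. These figures rest on a back-solved SD of 3.61 months and an unstated alpha taken as two-sided 0.05.

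A report of studies randomized, excluded with reason, and analysed in each arm, with the characteristics of those excluded, is what a competent analyst would produce unprompted, and it leaves the primary set and test untouched. Moving the check ahead of randomization depends on site routing information that the documents do not describe. Restoring trainee-read studies trades real panel effort for an estimate in a population the protocol chose not to study. Keeping the criteria-based set is a fair choice, and what is missing is reporting detail.
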